# 1. Protocol Synopsis

Title	Incidence and risk of heart failure in patients following metal-on-metal (MoM) hip arthroplasty	
Study Objectives	Co-Primary: To estimate the incidence and evaluate the risk of heart failure among patients undergoing MoM arthroplasties of the hip compared with those with alternative types of arthroplasties (non-MoM)	
	Co-Primary: To estimate the incidence and evaluate the risk of heart failure among patients undergoing MoM arthroplasties of the hip compared with age and gender similar Osteoarthritis (OA) cohort without arthroplasty	
Data Sources	Medicare SAF	
Study Design	Retrospective Cohort Study	
Study Population	Patients are eligible if they are (1) ≥ 65 years, (2) undergo an elective, primary total hip arthroplasty (THA) performed in the inpatient setting between October 1, 2005, and December 31, 2017 (index procedure), and (3) enrolled in the data source for at least 365 days prior to index procedure (baseline period). Patient exclusions include a diagnosis of heart failure, THA/TKA arthroplasty, or metal implants during the baseline period or concurrent diagnosis of hip fracture during the index THA procedure.	
Endpoints	2 recorded Heart Failure-related diagnosis codes	
Data Analyses	Descriptive statistics on baseline characteristics with comparison between exposure groups; Unadjusted incidence rate for heart failure; Propensity scores; Cox Regression to determine HRs with 95% Cl	

# 2. List of Abbreviations

Definition
Total Knee Arthroplasty
Total Hip Arthroplasty
Metal-on-Metal
Hazard Ratio
Confidence Interval
Rheumatoid Arthritis
Disease-modifying antirheumatic drugs
Osteoarthritis

# 3. Rationale and Background

It is estimated that the incidence of joint replacement is over 1 million total hip and total knee replacement procedures each year in the United States. With the aging of the "baby boomers," higher rates of diagnosis and treatment of advanced arthritis, and growing demand for improved mobility and

quality of life, the annual procedure volumes are projected to increase considerably in the future, making joint replacements the most common elective surgical procedures in the coming decades. The prevalence of total hip replacement in the United States was projected by Kremers et al in a 2015 publication. The authors reported the 2010 prevalence of total hip replacement in the U.S. population was 0.83% for the overall population and 2.34% in those 50 years of age and older. The prevalence of hip replacement was higher among women (0.93%) than among men (0.72%) and increased with age, reaching 1.49%, 3.25%, and 5.26% at sixty, seventy, and eighty years, respectively. These estimates corresponded to 2.5 million individuals (1.4 million women and 1.1 million men) with total hip replacement in 2010.

A study published by Gillam et al. in 2017 described a retrospective cohort study using data from the Australian Government Department of Veterans' Affairs health claims database on patients who received conventional THA for osteoarthritis between 2004 and 2012. The MoM THAs were classified into groups: Articular Surface Replacement (ASR) XL Acetabular System, other large-head (LH) (> 32 mm) MoM, and small-head (SH) ( $\leq$  32 mm) MoM. The primary outcome was hospitalization for heart failure after THA and included 4,019 patients with no history of heart failure (56% women). Men with an ASR XL THA had a higher rate of hospitalization for heart failure than men with MoP THA (hazard ratio (HR) = 3.2, 95% CI: 1.6–6.5). No statistically significant difference in the rate of heart failure was found with the other LH MoM or SH MoM compared to MoP in men. There was no statistically significant difference in heart failure rate between exposure groups in women.

Another study published by in January of 2018 described a linkage study between the National Joint Registry, Hospital Episodes Statistics and records of the Office for National Statistics on deaths. Patients who underwent elective total hip arthroplasty between January 2003 and December 2014 with no past history of cardiac failure were included and stratified as having either a MoM (n = 53 529) or a non-MoM (n = 482 247) arthroplasty. The primary outcome measure was the time to an admission to hospital for cardiac failure or death. Analysis was carried out using data from all patients and from those matched by propensity score. The risk of cardiac failure was lower in the MoM cohort compared with the non-MoM cohort (adjusted hazard ratio (aHR) 0.901; 95% confidence interval (CI) 0.853 to 0.953). The risk of cardiac failure was similar following matching (aHR 0.909; 95% CI 0.838 to 0.987) and the findings were consistent in subgroup analysis.

Goodnough et.al. published a study designed to compare the rate of onset of new cardiac symptoms in patients who have undergone MoM THA with those who have undergone metal-on-polyethylene (MoP) THA. Data from the Medicare Standard Analytics Files database for patients who underwent MoM THA between 2005 and 2012 was used. Bearing surface was selected using International Classification of Diseases ninth revision codes. Patients with a minimum five-year follow-up were selected. An age and gender-matched cohort of patients, who underwent MoP THA served as a comparison group. New diagnoses of cardiac disease including congestive heart failure were collected during the follow-up period. We identified 29 483 patients who underwent MoM THA and 24 175 matched patients who underwent MoP THA. Both groups had a mean Charlson comorbidity index score of 4. There were no statistically significant differences in 30 of 31 pre-existing comorbidities. Patients undergoing MoM THA had a slightly lower incidence of cardiac failure compared with those undergoing MoP THA at three years (6.60% versus 7.06%, odds ratio (OR) 0.93, 95% confidence interval (CI) 0.87 to 0.99) and four years (8.73% versus 9.49%, OR 0.91, 95% CI 0.86 to 0.97) postoperatively, with no difference in the incidence of new cardiac failure in between the groups at five years. There was no statistically significant difference in the incidence of arrhythmia, myocardial infarction and cardiomyopathy at any time between the two groups.

This study is being executed to elucidate the association between MoM vs non-MoM hip arthroplasties on subsequent diagnosis of heart failure. This study is device-agnostic in that all MoM and non-MoM devices, regardless of manufacturer, are being included.

## 4. Research Questions and Objectives

### 4.1 Research Question

Are patients with Metal-on-Metal arthroplasties of the hip at an increased risk of developing heart failure?

## 4.2 Research Objectives

#### 4.2.1 Primary objective(s):

- To estimate the incidence and evaluate the risk of heart failure among patients undergoing MoM arthroplasties of the hip compared with those with alternative types of arthroplasties (non-MoM)
- To estimate the incidence and evaluate the risk of heart failure among patients undergoing MoM arthroplasties of the hip compared with an age and gender similar Osteoarthritis cohort without arthroplasty

#### 4.2.2 Secondary objective(s):

• To describe and compare the baseline characteristics of the exposure groups and to identify important prognostic variables that should be balanced between the exposure groups and which should be included in the propensity score of the primary analysis.

[figure not shown]
## 5. Research Methods

### 5.1 Data Source

The Medicare Database (Medicare SAF) captures the majority of the US population age 65 or older. The limited dataset that will be utilized for this analysis includes Medicare Part A and Part B claims which captures Fee-for-Service. Medicare Advantage Patients are not captured. Medicare Part A captures inpatient hospital visits and related claims including diagnosis (ICD-9), procedures, Medicare Severity Diagnosis Related Group (MS-DRG), dates of service, hospital provider number, and beneficiary demographic information. Medicare Part B is available for institutional outpatient providers only. Examples of institutional outpatient providers include hospital outpatient departments, rural health clinics, renal dialysis facilities, outpatient rehabilitation facilities, comprehensive outpatient rehabilitation facilities, and community mental health centers. Available data elements include diagnosis (ICD-9), Healthcare Common Procedure Coding System (HCPCS), dates of service, outpatient provider number, revenue center codes, and beneficiary demographic information. Once an individual enrolls in Medicare they generally remain enrolled until death; hence, this database is robust for longitudinal studies.

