#### 5.2.1 Inclusion criteria

THA patients must meet ALL the following criteria to be included in study:

- Elective, primary THA performed in inpatient setting (first occurrence is the index date)
- >65 years
- Enrolled in the data source for at least 365 days prior to index procedure (baseline period)

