#### Age and gender-similar OA patients must meet ALL the following criteria to be included in study:

- > 2 recorded OA-related diagnosis codes:
- Code list
- >65 years
- Enrolled in the data source for at least 365 days prior index procedure (baseline period)

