#### 5.3.2.3 Patient Clinical Characteristics

- Deyo-Charlson Comorbidity Index (CCI): the CCI is an aggregate measure of comorbidity created by using select diagnoses associated with chronic disease (e.g., heart disease, cancer). Higher scores are indicative of greater comorbid burden. The CCI includes 19 medical conditions and weights these conditions from +1 to +6.
- Elixhauser comorbidity system: the Elixhauser comorbidity system is a set of 30 comorbidity indicators that is used for adjustment of comorbidity in observational studies. Van Walraven and colleagues developed a summary score for the Elixhauser comorbidities by modeling in-hospital mortality with inpatient admission data. The summary score is a weighted combination of the 30 Elixhauser comorbidities, where a larger comorbidity weight indicates a stronger association between the comorbidity and in-hospital mortality.
- Medicare Enrollment State Buy-In Status (Yes/No)
- Individual Elixhauser and Charlson comorbidity categories:
  - Specific CV comorbidities: dyslipidemia, hypertension, diabetes, peripheral vascular disease, TIA and obesity
- Other comorbidities that have been associated with increased mortality such as: chronic obstructive pulmonary disease, obstructive sleep apnea, cardiac arrhythmias, HIV, and cancer
- Rheumatoid Arthritis, Psoriatic Arthritis, Osteoporosis and Osteopenia
- Dislocation and instability post index
- Metalosis post index

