#### 5.3.3 Outcome(s) or Dependent Variable(s)

#### 5.3.3.1 Outcomes for Primary Objective(s) – Primary Endpoint

- Heart failure cases diagnosed in the first 30-days post implantation (index date) will be excluded to prevent including cases of iatrogenic fluid overload due to the surgical procedure
- > 2 recorded acute heart failure-related diagnosis codes

ICD-9-CM Code	Code Description
428.0	Congestive heart failure, unspecified
428.1	Left heart failure
428.20	Systolic heart failure, unspecified
428.21	Systolic heart failure, acute
428.23	Systolic heart failure, acute on chronic
428.30	Diastolic heart failure, unspecified
428.31	Diastolic heart failure, acute
428.33	Diastolic heart failure, acute on chronic

428.40	Combine systolic and diastolic heart failure, unspecified
428.41	Combine systolic and diastolic heart failure, acute
428.43	Combine systolic and diastolic heart failure, acute on chronic
428.9	Heart failure, unspecified

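### MoM and OA patients are selected and observed differently in institutional claims, and no listed covariate measures a patient's prior use, so the second co-primary hazard ratio is likely biased, more plausibly toward no harm.

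*Protocol*

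**What the plan says.** **Data.** Section 5.1 describes two sources. For inpatient care, "Medicare Part A captures inpatient hospital visits and related claims including diagnosis (ICD-9), procedures". For outpatient care, "Medicare Part B is available for institutional outpatient providers only". The second source is wider than hospitals: "Examples of institutional outpatient providers include hospital outpatient departments, rural health clinics, renal dialysis facilities, outpatient rehabilitation facilities".

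**Entry.** Section 5.2.1 admits OA patients on a count of "2 recorded OA-related diagnosis codes" (printed with a greater-than sign that may have been greater-or-equal). It sets no care setting, diagnosis position or time window for those codes. THA patients enter at their first elective primary THA in the inpatient setting. Both cohorts need 365 days of prior enrolment, and section 5.2.2 removes patients with heart failure recorded in that period.

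**Outcome.** The primary endpoint in section 5.3.3.1 is a repeated count of acute "heart failure-related diagnosis codes", found in the same claims.

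**Adjustment.** Section 5.4.3 uses propensity score matching or stratification. (It names RA patients as the second comparator; I read this as the OA cohort of section 4.2.1.) The listed variables cover demographics, the index procedure, comorbidity (for example, "Deyo-Charlson Comorbidity Index (CCI): the CCI is an aggregate measure of comorbidity"), state buy-in status, and hospital and surgeon features. Section 4.2.2 leaves the final choice of propensity score variables to the baseline description, and section 5.3.3.3 defines the variables for that objective as those already listed.

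**The concern.** Institutional contact plays a part at three points: it makes an OA patient visible, it produces the heart failure codes that form the endpoint, and it determines how completely baseline heart failure and comorbidity are recorded. An OA patient must have had OA recorded repeatedly in facility claims, possibly as a secondary diagnosis during care for something else. A MoM patient needs only the one operation.

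If the OA cohort therefore holds more heavy users of institutional care, it may have both a higher underlying heart failure risk and a higher chance of having heart failure recorded. Either would lower the MoM versus OA hazard ratio. This is one of two co-primary contrasts in a safety question, so the consequence to avoid is a real excess in MoM patients being masked.

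**Working it through.** **1. Is prior use measured anywhere?** The nearest listed items are these:
- Length of stay (5.3.2.3's neighbour, section 5.3.2.2) is a procedural characteristic. It describes the index stay, which OA patients do not have.
- Hospital and surgeon volume (5.3.2.4) describe the provider, not the patient.
- Charlson, Elixhauser and the individual comorbidities (5.3.2.3) reflect illness as recorded in the same claims. They are related to use but do not count it.

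No item counts a patient's own admissions or outpatient claims. Among the sensitivity analyses in 5.4.4, none changes how OA patients are found. Section 5.6 mentions misclassification in general but not this difference.

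**2. Selection effect.** The protocol has no figure to reproduce, so all inputs in this step are assumptions. Let m and h be the shares of frequent institutional users in MoM and OA, and k their recorded heart failure rate ratio after comorbidity adjustment. When the true hazard ratio is 1, the apparent value is approximately

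(1 + m(k − 1)) / (1 + h(k − 1)).

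With m = 0.2:
- h = 0.2, any k: 1.00
- h = 0.3, k = 1.5: 1.10/1.15 = 0.957
- h = 0.4, k = 2.0: 1.20/1.40 = 0.857
- h = 0.5, k = 2.5: 1.30/1.75 = 0.743

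A true hazard ratio of 1.20 would appear as 1.15, 1.03 and 0.89 in the last three cases.

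**3. Detection effect.** For a fairly uncommon outcome, the factor is roughly the ratio of sensitivities, MoM over OA. Assumed values of 0.7 versus 0.8 give 0.875, and 0.6 versus 0.8 give 0.75.

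**4. Opposing effect.** Baseline heart failure is also found through these claims, so less-observed MoM patients keep more unseen prevalent cases. With prevalence p and sensitivity s, the unseen share is u = p(1 − s) / (p(1 − s) + 1 − p). The recorded risk is then u·c + (1 − u)·i. Here i = 0.0873, the four-year MoM risk in the Medicare SAF study cited in section 3, and c is the assumed share of unseen cases that are later recorded.

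For p = 0.08, c = 0.8 and s = 0.7 (MoM) versus 0.8 (OA):
- MoM: u = 0.024/0.944 = 0.0254, risk 0.1054
- OA: u = 0.016/0.936 = 0.0171, risk 0.0995
- Ratio: 1.06

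With s = 0.6 versus 0.8 the ratio is 1.118. Over p = 0.04 to 0.12, c = 0.5 to 0.8 and the unequal sensitivity pairs tried (0.7 versus 0.8, 0.6 versus 0.8, 0.7 versus 0.9), it runs from 1.02 to 1.19.

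**5. Combining them.** Detection and incomplete exclusion together give 0.875 × 1.06 = 0.93 and 0.75 × 1.118 = 0.84, still toward no harm. Mild selection with incomplete exclusion but no detection difference gives 0.957 × 1.06 = 1.01, so the sign is not guaranteed. Under-recorded comorbidity in MoM patients also pushes upward and is not sized here.

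**6. Scale against precision.** Section 5.3.4 cites 18,521 MoM patients. Assuming 1:1 matching, about four years of follow-up and the 8.73% risk in both arms, events are 2 × 18,521 × 0.0873 = 3,234. Power at two-sided 5% (assumed) is Φ(|ln HR| × √3,234 / 2 − 1.96). This gives 85% for a hazard ratio of 0.90 and 77% for 1.10. A bias factor near 0.90 is therefore of the same size as the effects the study could detect.

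**The case against.** The strongest reply is that the protocol does not close the propensity score model. Section 4.2.2 leaves variable selection open, the SAP is not at hand, and comorbidity scores drawn from the same claims rise with contact and so absorb part of the difference. This stands in part: a reader might infer that the propensity score cannot remove the imbalance, and the documents do not say that. But the candidate pool in 5.3.2.1 to 5.3.2.4 contains no utilisation measure, and the comorbidity record depends on the very contact that differs.

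A second reply is that section 5.4.4 already restricts the outcome to heart failure hospitalisation, which Part A should capture in every cohort. That may reduce the detection effect. It leaves selection and incomplete baseline exclusion untouched.

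Three stronger readings are tempting and are not supported:
- That OA patients managed in an office can never enter. They can, through any facility visit where OA is coded, including rehabilitation. With no time window on the codes, qualifying need not mean frequent use.
- That the contrast is known to be biased toward no harm. The documents hold no utilisation data, and step 4 of the working gives an effect in the opposite direction.
- That both co-primary contrasts are affected. MoM and non-MoM patients share one entry route, so this mechanism does not apply to that comparison.

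**Conclusion.** The point holds for MoM versus OA. Entry and outcome ascertainment differ between the two cohorts by design, and the plan lists nothing that measures the difference directly. Bias in this hazard ratio is likely, with toward no harm the more plausible direction rather than an established one. Under the assumed shares and rate ratios, the apparent hazard ratio at a true value of 1 runs from 1.00 to about 0.74 before the opposing effects, which in the cases tried multiply it by 1.02 to 1.19. Only the 8.73% and the 18,521 come from the protocol; every other input is assumed. The case for change rests on the differing entry rules and the missing covariate, not on any one of these figures.

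**What to change.** - For the MoM versus OA contrast, add two variables to section 5.3.2.3 and include them in the propensity score: the number of inpatient stays and the number of institutional outpatient claim days in the 365-day baseline. Exclude the index THA claim and the OA-qualifying claims, so that the entry rule does not itself inflate the OA count. This requires an explicit OA index date, because section 5.2.1 anchors the OA baseline to an index procedure that these patients do not have.
- Add to section 5.4.4 a sensitivity analysis requiring comparable baseline institutional contact in both cohorts, optionally limited to OA patients with OA as principal diagnosis on the qualifying claims.
- State in section 5.6 that OA patients are visible only through institutional claims, and that the direction of the resulting bias is uncertain.

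The cost is two covariates derived from claims already held, one extra run, and somewhat fewer matched OA patients.

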## 5.2 Study Design

This is a retrospective cohort study of patients undergoing total hip arthroplasty or have a diagnosis of OA without arthroplasty and meeting the inclusion and exclusion criteria between October 1, 2004, and June 30, 2018 (study period). The enrollment period (identification of index date) is between October 1, 2005 and December 31, 2017. The identified patients are longitudinally followed until a diagnosis of heart failure, THA revision (arthroplasty cohort only), new total knee arthroplasty (TKA) or THA, end of enrollment, death, or end of the study, whichever occurs first. The graphic below provides a visual representation of the study design.

\*Heart failure diagnosed within 30-days of index date will be excluded to prevent cases of iatrogenic fluid overload due to the surgical procedure

#### 5.2.1 Inclusion criteria

THA patients must meet ALL the following criteria to be included in study:

- Elective, primary THA performed in inpatient setting (first occurrence is the index date)
- >65 years
- Enrolled in the data source for at least 365 days prior to index procedure (baseline period)

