#### 5.2.2 Exclusion criteria

THA patients meeting any of the following during the 365-day baseline period will be excluded from the study:

- Diagnosis code for acute or chronic heart failure
- TKA or THA surgery (primary or revision)
- Concurrent (with index procedure) diagnosis of hip fracture

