# Age and gender-similar OA patients meeting any of the following during the 365-day baseline period will be excluded from the study:

- Diagnosis of acute or chronic heart failure
- TKA or THA surgery (primary or revision)
- Arthroscopic surgery

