#### 5.3.1 Primary Independent Variable(s) – Exposure Groups

- Group 1: Metal-on-Metal total hip arthroplasty
  - o ICD-9: 00.75, hip bearing surface, metal-on-metal
  - o ICD-10 Codes:
    - OSRR01Z, Replacement of Right Hip Joint, Femoral Surface with Metal Synthetic Substitute, Open Approach
    - OSRS01Z, Replacement of Left Hip Joint, Femoral Surface with Metal Synthetic Substitute, Open Approach
    - OSRS019, Replacement of Left Hip Joint, Femoral Surface with Metal Synthetic Substitute, Cemented, Open Approach
    - OSRS01A, Replacement of Left Hip Joint, Femoral Surface with Metal Synthetic Substitute, Uncemented, Open Approach
- Group 2: Non-Metal-on-Metal total hip arthroplasty
  - o ICD-9 Codes
    - 00.74, hip bearing surface, metal-on-polyethylene (MoP)
    - 00.76, hip bearing surface, ceramic-on-ceramic (CoC)
    - 00.77, hip bearing surface, ceramic-on-polyethylene (CoP)
  - o ICD-10 Codes:
    - OSRR03Z, Replacement of Right Hip Joint, Femoral Surface with Ceramic Synthetic Substitute, Open Approach
    - OSRS03Z, Replacement of Left Hip Joint, Femoral Surface with Ceramic Synthetic Substitute, Open Approach
    - OSRS039, Replacement of Left Hip Joint, Femoral Surface with Ceramic Synthetic Substitute, Cemented, Open Approach
    - OSRS03A, Replacement of Left Hip Joint, Femoral Surface with Ceramic Synthetic Substitute, Uncemented, Open Approach
- Age and gender-similar OA patients

Introduced in October 2005, ICD-9 bearing surface code identifiers (00.74 for Metal on p, 00.75 for M-M, 00.76 for C-C, 00.77 C-PE) are optional modifiers that can be reported in conjunction with the primary procedure code for total hip arthroplasty. A limitation on this data is that it has been shown to have both under-coding and misclassification when coded.

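### In the second co-primary comparison, MoM patients may have any elective, non-fracture indication while controls must have OA, so part of the hazard ratio can reflect the reason for surgery

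*Protocol*

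**What the plan says.** The second co-primary objective (4.2.1) sets MoM patients "compared with an age and gender similar Osteoarthritis cohort without arthroplasty".

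- **MoM arm.** Section 5.2.1 lists three criteria for THA patients: the operation ("Elective, primary THA performed in inpatient setting (first occurrence is the index date"), age, and a year of prior enrollment. Section 5.3.1 then assigns patients to the MoM group by procedure code, for example "ICD-9: 00.75, hip bearing surface, metal-on-metal". None of these is a diagnosis. Among the THA exclusions in 5.2.2, the only one that concerns the indication is "Concurrent (with index procedure) diagnosis of hip fracture".
- **Controls.** Section 5.2.1 requires "> 2 recorded OA-related diagnosis codes", with no stated look-back window for those codes. Section 5.2.2 also excludes controls with "Arthroscopic surgery" in the baseline year. That item appears neither in the THA exclusions nor in those common to both groups.
- **Adjustment.** Section 5.4.3 plans a propensity score, used for matching or stratification. Section 4.2.2 leaves its content to be chosen from the baseline comparison. The listed characteristics in 5.3.2.3 include "Rheumatoid Arthritis, Psoriatic Arthritis, Osteoporosis and Osteopenia".
- **Comparator in the model.** Section 5.4.3 names RA patients, not OA patients, as the group without arthroplasty.

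**The concern.** The contrast is meant to compare people with OA who received a MoM hip with people with OA who did not have arthroplasty. As written, OA is universal in one arm and optional in the other. An elective THA for inflammatory arthritis, osteonecrosis or another non-OA cause enters the MoM arm if the bearing code is present. If such patients have a different underlying heart failure risk, the hazard ratio carries that difference together with any effect of the implant. This is a co-primary estimate, and under 5.4.3 a significantly higher risk in MoM patients leads to further modelling of risk factors.

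The arthroscopy exclusion is a second, smaller asymmetry in the same comparison: it removes controls but not MoM patients, and no reason is given.

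**Working it through.** **Reading the text.**

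| | MoM arm | OA controls |
|---|---|---|
| OA diagnosis (5.2.1) | not required | repeated codes required |
| Indication removed (5.2.2) | concurrent hip fracture | not applicable |
| Arthroscopy in baseline year (5.2.2) | allowed | excluded |

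Nothing elsewhere closes the gap. The three sensitivity analyses in 5.4.4 narrow the outcome to hospital admissions, split by coding system, and drop metal-on-polyethylene hips from the non-MoM group. None restricts MoM patients to OA. Section 5.6 does not mention the difference.

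**Size.** The protocol has no figure to reproduce: 5.3.4 gives only a count of 18,521 MoM patients, with no alpha, power or target effect. What follows is an illustration.

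Inputs, both assumed and not in the documents:
- p, the share of MoM patients without OA: 5% to 15%.
- r, their heart failure hazard relative to MoM patients with OA: 1.2 to 2.0. The documents do not give the direction either; with r below 1 the bias would run the other way.

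With a true implant HR of 1 and no adjustment, the apparent HR is approximately (1 - p) + p × r = 1 + p(r - 1).

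| p | r = 1.2 | r = 1.5 | r = 2.0 |
|---|---|---|---|
| 5% | 1.010 | 1.025 | 1.050 |
| 10% | 1.020 | 1.050 | 1.100 |
| 15% | 1.030 | 1.075 | 1.150 |

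If the rheumatoid and psoriatic arthritis covariates removed half of the non-OA share (also assumed), the formula becomes 1 + (p/2)(r - 1):
- p = 5%: 1.005 to 1.025
- p = 10%: 1.01 to 1.05
- p = 15%: 1 + 0.075 × 0.2 = 1.015, to 1 + 0.075 × 1.0 = 1.075

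**Chance of a false signal.** Assume 18,521 patients per arm (1:1) and the MoM heart failure risks that section 3 cites from an earlier Medicare study, 6.60% at three years and 8.73% at four. Expected events are 2 × 18,521 × 0.066 = 2,445 and 2 × 18,521 × 0.0873 = 3,234. By Schoenfeld's formula with two-sided alpha 0.05, the chance of a significant result in the harmful direction is Φ(√(D/4) × ln HR - 1.96):

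| Apparent HR | D = 2,445 | D = 3,234 |
|---|---|---|
| 1.02 | 7% | 8% |
| 1.05 | 23% | 28% |
| 1.10 | 65% | 77% |

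With no bias this chance would be 2.5%. A shift of 1.02 hardly matters. One of 1.05 to 1.10 would, because the cohort is large enough to declare it significant.

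**The case against.** **The MoM arm is not open to every indication.** The operation must be elective and primary, and concurrent hip fracture is excluded. This stands; the point concerns elective, non-fracture indications only.

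**Adjustment is planned.** A reader might infer that no propensity score could help, because every control has OA and non-OA MoM patients therefore have no counterpart. The documents do not support that. Rheumatoid and psoriatic arthritis are listed, and nothing bars controls who have OA together with either, so such MoM patients can be matched or stratified on those conditions. Matching may also drop patients who find no match. The covariate list is partly open-ended, and a SAP may fix the score. What remains is that OA as the indication and other non-OA indications are not listed, and that choosing covariates later does not change who is eligible.

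**The size is assumed.** This stands. It is also tempting to set the illustrated bias against the ratios of about 0.90 to 0.93 cited in section 3. Those come from MoM versus other bearings, and section 3 also cites an HR of 3.2 in one device subgroup of men, so they are no benchmark for this contrast.

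**The bearing question has its own comparison.** A reader might conclude that the study as a whole could mistake indication for a metal effect. MoM versus non-MoM applies the same THA criteria to both arms, so this asymmetry does not arise there. The second comparison sets operated against unoperated patients, and selection for surgery stays in it whatever is done about OA.

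**Precedent is mixed.** The Australian study in section 3 took THA for osteoarthritis; the other two studies are described without that restriction. Precedent settles nothing.

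**Conclusion.** The asymmetry is in the eligibility text and affects the second co-primary comparison only. Part of that hazard ratio can reflect a non-OA reason for surgery, and the planned adjustment may reduce this without clearly removing it. On the assumed inputs, the spurious HR under no implant effect is about 1.01 to 1.15 unadjusted and smaller after adjustment. It is negligible if few MoM patients lack OA. It is material if 10% or more do and their heart failure risk is clearly higher. Neither quantity is in the documents. The gap itself is certain and its size is not, so this is an inexpensive improvement worth making, not a flaw that invalidates the study.

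The statement that every control has OA follows the objectives and 5.2.1. The RA comparator in 5.4.3 contradicts it, and the passages must be reconciled.

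**What to change.** 1. **Section 5.2.1, for MoM versus OA only:** require an OA diagnosis in the MoM arm. Write the code rule and look-back window identically for both arms, and count the index THA claim for MoM patients. MoM versus non-MoM can keep all elective indications.
2. **Section 5.4.4:** report the unrestricted MoM arm as a sensitivity analysis.
3. **Section 5.2.2:** apply the baseline arthroscopy exclusion to both arms of this comparison or to neither.
4. **Section 5.4.3:** reconcile the RA comparator with the OA cohort in 4.2.1 and 5.2.1.
5. **Section 5.6:** state that selection for surgery remains in this contrast. The OA restriction sets p to 0, which brings only the indication component to 1.00.

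**Cost.** One filter on claims already held, and some loss of precision in one comparison. The loss will exceed the true non-OA share: section 5.1 says Part B is available for institutional outpatient providers only, so some MoM patients who do have OA will lack the codes. Counting the index claim limits this, and the unrestricted sensitivity analysis shows whether it matters.
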